It is important to note that the sequential model building process used to identify an analysis data set for which there is adequate covariate balance within subclasses, poses no concern for Type I error inflation. This is because the PS model building process makes no use of outcome data. To avoid bias, no outcome data will be provided to the statistician ([name]) who will be forming the PS sub classes; and the model identification process will be documented in a series of iterations as described in [Maislin and Rubin 2011]. That is, the sequential model-building heuristic should be viewed as part of the 'design of the observational study'. Here 'design' may be interpreted as "contemplating, collecting, organizing, and analyzing of data that takes place prior to seeing any outcome data (Rubin 2008)". At its conclusion, verification of balance between device groups within sub class is easily done through graphical means.

Given the expected similarity of the populations from which the investigational and control groups were obtained and the specificity of the clinical indication, it is expected that no more than 20% of the ACDF historical controls and 10% of the investigational device group will need to be excluded in order to identify sub classes that meet the Rubin criteria for validity.

We acknowledge that because the proposed propensity score design can only assess the comparability of the two groups after the current study has been completed, there can be significant risk that in the end the data may not be comparable. The sample size determination assumes that at most 20% of the ACDF historical and at most 10% of the investigational device patients will be excluded in the iterative heuristic used to construct PS sub classes that meet Rubin's validity criteria. The risk of insufficient sample sizes due to such exclusion can be reduced, by continuing enrollment into the investigational device group. For example, suppose a valid PS design is identified that excludes many more controls than expected but excluded only a very tiny fraction of investigational device patients. Then, the reduction in power due to a smaller control group sample size can be recovered by

---

25 Rubin D. For objective causal inference, design trumps analysis. *The Annals of Applied Statistics* 2008, 2:3:808-840.

continuing enrollment into investigational arm until the original power target is maintained and then performing a new sub classification.

All components necessary to formulate the relevant composite clinical endpoints are available in both studies. Any differences in endpoint evaluation are due to the nature of the difference between artificial discs and fusion procedures. The components of the CCS were evaluated in the same fashion for the ACDF control as they are to be evaluated prospectively for Simplify® Disc enhancing comparability of results from the two studies. This includes use of the same independent radiography core, [REDACTED]. Although composite clinical success requires a threshold improvement in the Neck Disability Index (NDI), the “NDI is the oldest and most widely used instrument for self-reporting of disability due to neck pain. Its internal psychometric properties have been well established in numerous cultural groups with neck pain: it is highly reliable, strongly internally consistent, and with a 1-factor structure for “physical disability.” It has strong and well-documented convergent and divergent validity with other instruments used in the evaluation of patients and subjects with neck pain” (Vernon 2008). The minimum clinically important difference in cervical spine fusion surgery was established to be 15 points out of 100 (Carreon, Glassman and Campbell 2010).

In summary, the above factors lead to the reasonable expectation that the design of the observational study using PS sub classes will result in statistical estimates of treatment group differences with acceptably low bias.

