#### 2.2.6.4 SAMPLE SIZE ANALYSIS

For the control group, prior analysis utilized an endpoint that was summarized as follows: “Overall success requires success on each component including: 15 point improvement in NDI score, no device failure, no supplemental index surgery failure, no major adverse event, and no neurological deterioration (assessed through 24 months only).” These results were used to

---

 Vernon H. The Neck Disability Index: State of the Art 1991-2008. *Journal of Manipulative and Physiological Therapeutics* 2008, September 491-502.

inform the sample size justification since the endpoint is similar to the endpoint to be used in the proposed study. At Month 24, 116 of 133 (87.2%) ACDF controls were evaluable for Month 24 CCS and 78 of these 116 (67.2%) achieved Month 24 CCS. For the Kineflex|C investigational arm, 118 of 136 (86.7%) patients were evaluable for overall success and overall success was achieved in 95 of 118 (80.5%) patients and 82 of 116 (70.7%), respectively. For the purpose of sample size determination, it was assumed that patients implanted with the Simplify® Disc would have an expected Month 24 overall success rate equal to 80.5%, the value observed for the Kineflex|C group at Month 24.

As noted above, the fusion component of the composite clinical success endpoint is removed from the primary endpoint. A re-analysis of the final data set was performed with the aim of determining the numbers and percentages of patients achieving the composite endpoint with the fusion component removed from both device groups. It was observed that for Kineflex|C, the success rate increased only slightly from 80.5% (95/118) to 81.4(%). In contrast, for the fusion control group to be used in the current study, the success rate increased from 67.2% (78/116) to 74.1 (%). The estimated device group difference was reduced from 13.3% to 7.3%.

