It is assumed for the purpose of sample size analysis that at least 80% of the 116 evaluable ACDF controls, that is, N=93 will be remaining after the iterative PS sub classes determination and that the success rate will be 74.1% in the retained sample. It is possible that the effective sample size will be slightly higher since, as described below, multiple imputation will be used to address missing data from the prior study.

In order to have a sufficient size sample for safety profile evaluation, 150 investigational device patients will be enrolled. For the purpose of sample size evaluation, this value is reduced by 15% to account for loss-to-follow-up. It is further assumed that no more than 10% of the analysis set will be excluded based on design of the PS sub classes, reducing the evaluable sample size from 128 to 115.

The assumptions above imply an expected device group difference equal to equal to 7.3% for the primary endpoint. The study is designed to demonstrate non-inferiority using a non-inferiority margin equal to -10.0%.

If there were N=115 Simplify® Disc patients, then a “two-group large-sample normal approximation test of proportions with a one-sided 0.05 significance level will have 91% power to reject the null hypothesis that the test and the standard are not equivalent (the difference in proportions,  $\pi_1 - \pi_2$ , is -

0.10 or farther from zero in the same direction) in favor of the alternative hypothesis that the proportions in the two groups are equivalent, assuming that the expected difference in proportions is 0.073 and the proportion in the standard group is 0.741 [REDACTED]).

Thus, as long as the superiority margin between the Simplify® Disc and ADCF about the same as observed between Kineflex|C and ADCF, then N=115 patients included in the Simplify® Disc analysis set will result in adequate (i.e.,  $\geq 80\%$ ) statistical power. As noted above, this sample size is conservatively increased by 15% to account for potential loss-to-follow-up and by 10% to account from exclusions during the PS modeling. Therefore, the target prospective enrollment is N=150.

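### Does the unnumbered "original power target" for extending enrolment leave the sample-size plan unworkable?

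*Combined protocol and SAP*

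**What the plan says.** Section 2.2.6.3 plans for propensity-score exclusions of at most 20% of controls and 10% of device patients. It then addresses heavier losses: "The risk of insufficient sample sizes due to such exclusion can be reduced, by continuing enrollment into the investigational device group". The case it imagines is a valid design that "excludes many more controls than expected but excluded only a very tiny fraction of investigational device patients". In that case "the reduction in power due to a smaller control group sample size can be recovered by" further enrolment in the device arm, namely "continuing enrollment into investigational arm until the original power target is maintained", followed by a new subclassification. No percentage is attached to the target.

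Section 2.2.6.4 first states that Simplify patients "would have an expected Month 24 overall success rate equal to 80.5"%, the Kineflex|C result on the earlier endpoint. The next paragraph removes fusion from the endpoint and reports that for Kineflex|C "the success rate increased only slightly from 80.5% (95/118) to 81.4"%, while the ACDF rate rose from 67.2% to 74.1%. For controls it then assumes "that the success rate will be 74.1% in the retained sample", and concludes: "The assumptions above imply an expected device group difference equal to equal to 7.3% for the primary endpoint".

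The same section sets enrolment at 150 for safety evaluation and reduces that to 115 evaluable after 15% loss and 10% exclusion. It gives 91% power against 93 controls and ends by describing 115 as adequate, glossed as at least 80%.

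**The concern.** A rule that continues enrolment until a power target is met needs a known target. Two figures stand close together in section 2.2.6.4. The verbs in section 2.2.6.3 (power is to be recovered and maintained) suggest the 91% that was calculated, while the closing remark on adequacy suggests 80%. Sections 2.2.6.9 and 2.2.6.10 are redacted and cannot settle the matter.

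The Simplify rate is also printed twice. The labelled 80.5% against 74.1% gives 6.4 points, not the 7.3 points said to follow from the assumptions.

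At stake would be whether enrolment stops at 150 or goes beyond it, and by how many patients receiving an investigational implant, if control losses are heavier than planned. Under the 91% reading the target might not be attainable at all within the limits of 16 sites and 24 subjects per site.

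**Working it through.** **Inputs.** From section 2.2.6.4: one-sided alpha 0.05, margin 0.10, control rate 0.741, difference 0.073 (so Simplify 0.741 + 0.073 = 0.814), 116 evaluable controls of whom 93 are retained, and 150 enrolled, giving 150 × 0.85 = 127.5 (printed as 128) and 127.5 × 0.90 = 114.75 (printed as 115).

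**Formula.** Unpooled normal approximation: power = Φ[(pT − pC + 0.10)/SE − 1.645], with SE² = pT(1 − pT)/nT + pC(1 − pC)/nC.

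**The plan's own figure.** SE² = 0.151404/115 + 0.191919/93 = 0.003380, so SE = 0.05814. Then 0.173/0.05814 = 2.976, and Φ(2.976 − 1.645) = 0.908. The printed 91% is right for the unstratified two-group test that the section names.

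**The labelled 80.5%.** SE = 0.05855, 0.164/0.05855 = 2.801, and Φ(2.801 − 1.645) = 0.876. This does not reproduce 91%, so the calculation was done with 81.4%. The matched pair from the old endpoint (80.5% vs 67.2%) gives 98.5%, which is not the printed figure either. The 80.5% sentence was simply not updated.

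**Where the two power readings part.** Take the situation in section 2.2.6.3: almost no device patients excluded, so 128 evaluable, with Simplify at 81.4%.

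| Controls retained (of 116) | Power with 128 Simplify |
|---|---|
| 93 | 91.8% |
| 86 | 90.6% |
| 85 | 90.4% |
| 80 | 89.4% |
| 70 | 86.8% |
| 65 | 85.2% |
| 53 | 80.3% |
| 52 | 79.8% |

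If 91% means any value that rounds to it (at least 90.5%), more patients are called for below 86 controls. If it means regaining the planned 90.8%, the cut-off is 88. An 80% target calls for more only below 53. The readings therefore differ from 53 to 85 retained controls, that is, with (116 − 85)/116 = 27% to (116 − 53)/116 = 54% excluded, against a planned maximum of 20%.

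**Size inside that band.** At 80 controls, 90.5% to 90.8% needs 148 to 155 evaluable, or 175 to 183 enrolled (dividing by 0.85): 25 to 33 beyond 150. At 70 controls it needs 222 to 238 evaluable, or 262 to 280 enrolled: 112 to 130 beyond 150. Under the 80% reading the extra number is zero in both cases.

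**Which reading the text supports.** Section 2.2.6.4 gives safety as the reason for 150, works down to 115, and reports the power that follows. The paragraph directly after the power statement concludes that 115 is adequate and defines adequate as at least 80%. So 80% acts as the criterion and 91% as a result that satisfies it; the two do not contradict each other. The sentence that opens the remedy in section 2.2.6.3 speaks of insufficient sample sizes, which fits an adequacy threshold. A literal 91.0% fits less well: with 93 controls it needs 118 analysed Simplify patients, so the plan's own 115 would just miss it.

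**The case for a change.** The strongest case for a change is that an extension decided after enrolment, in an unblinded study with a historical control, should rest on one number fixed in advance. To recover lost power most naturally means returning to what was lost, which is 91%. On that reading 70 retained controls would nearly double enrolment, and the cap of 16 × 24 = 384 subjects would put 91% out of reach at 64 or fewer controls, although power at 65 controls with 128 evaluable is still 85.2%.

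Some of this stands. The text names no number, two careful readers could differ, and the calculations are sound. The large figures, however, arise only under the reading the text supports less well, and only when exclusions exceed the plan's ceiling. The passage describes what can be done, in a worked supposition; it does not bind the sponsor to enrol until 91% is reached. The statistician forming the subclasses is given no outcome data, so the number of retained controls, which prompts any extension, carries no information about the treatment difference. A larger or smaller device arm chosen on that basis changes precision, not the validity of the non-inferiority test.

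On the rate, the objection is right that the 80.5% sentence is out of date. But the re-analysis paragraph and the power statement (0.073 and 0.741) leave only 81.4% as the working value.

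**Conclusion.** The concern does not call for a change. What remains is a missing number beside an illustrative option and one stale sentence. An analyst would sensibly take at least 80% as the threshold and 81.4% vs 74.1% as the rates. On that basis no extension is needed down to 53 retained controls with 128 evaluable Simplify patients, or 55 with 115.

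The 91% (90.8% recomputed), the enrolment of 150, the 10-point margin and the primary analysis are the same under either reading. Naming a target would record a sponsor preference; it would not improve the method. Correcting 80.5% to 81.4% would be editorial and would alter no result.

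This rests on the unstratified normal approximation that the plan itself uses, on its 15% loss assumption, and on the visible text, since two statistical subsections are redacted. It makes no claim about the power of the quintile-adjusted, multiply imputed test.

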#### 2.2.6.4 SAMPLE SIZE ANALYSIS

For the control group, prior analysis utilized an endpoint that was summarized as follows: “Overall success requires success on each component including: 15 point improvement in NDI score, no device failure, no supplemental index surgery failure, no major adverse event, and no neurological deterioration (assessed through 24 months only).” These results were used to

---

 Vernon H. The Neck Disability Index: State of the Art 1991-2008. *Journal of Manipulative and Physiological Therapeutics* 2008, September 491-502.

inform the sample size justification since the endpoint is similar to the endpoint to be used in the proposed study. At Month 24, 116 of 133 (87.2%) ACDF controls were evaluable for Month 24 CCS and 78 of these 116 (67.2%) achieved Month 24 CCS. For the Kineflex|C investigational arm, 118 of 136 (86.7%) patients were evaluable for overall success and overall success was achieved in 95 of 118 (80.5%) patients and 82 of 116 (70.7%), respectively. For the purpose of sample size determination, it was assumed that patients implanted with the Simplify® Disc would have an expected Month 24 overall success rate equal to 80.5%, the value observed for the Kineflex|C group at Month 24.

As noted above, the fusion component of the composite clinical success endpoint is removed from the primary endpoint. A re-analysis of the final data set was performed with the aim of determining the numbers and percentages of patients achieving the composite endpoint with the fusion component removed from both device groups. It was observed that for Kineflex|C, the success rate increased only slightly from 80.5% (95/118) to 81.4(%). In contrast, for the fusion control group to be used in the current study, the success rate increased from 67.2% (78/116) to 74.1 (%). The estimated device group difference was reduced from 13.3% to 7.3%.

It is assumed for the purpose of sample size analysis that at least 80% of the 116 evaluable ACDF controls, that is, N=93 will be remaining after the iterative PS sub classes determination and that the success rate will be 74.1% in the retained sample. It is possible that the effective sample size will be slightly higher since, as described below, multiple imputation will be used to address missing data from the prior study.

In order to have a sufficient size sample for safety profile evaluation, 150 investigational device patients will be enrolled. For the purpose of sample size evaluation, this value is reduced by 15% to account for loss-to-follow-up. It is further assumed that no more than 10% of the analysis set will be excluded based on design of the PS sub classes, reducing the evaluable sample size from 128 to 115.

The assumptions above imply an expected device group difference equal to equal to 7.3% for the primary endpoint. The study is designed to demonstrate non-inferiority using a non-inferiority margin equal to -10.0%.

If there were N=115 Simplify® Disc patients, then a “two-group large-sample normal approximation test of proportions with a one-sided 0.05 significance level will have 91% power to reject the null hypothesis that the test and the standard are not equivalent (the difference in proportions,  $\pi_1 - \pi_2$ , is -

0.10 or farther from zero in the same direction) in favor of the alternative hypothesis that the proportions in the two groups are equivalent, assuming that the expected difference in proportions is 0.073 and the proportion in the standard group is 0.741 [REDACTED]).

Thus, as long as the superiority margin between the Simplify® Disc and ADCF about the same as observed between Kineflex|C and ADCF, then N=115 patients included in the Simplify® Disc analysis set will result in adequate (i.e.,  $\geq 80\%$ ) statistical power. As noted above, this sample size is conservatively increased by 15% to account for potential loss-to-follow-up and by 10% to account from exclusions during the PS modeling. Therefore, the target prospective enrollment is N=150.

#### 2.2.6.5 PROPENSITY SCORE MODELING APPROACH

A sequential heuristic for PS modeling will be used to determine the PS model (Maislin and Rubin 2011). The heuristic is capable of producing balance between groups that are prerequisite for valid efficacy comparisons. The heuristic includes a trio of "stages" that may be repeated as many times as necessary. These stages include (1) estimating a main effects PS model; (2) identification of required higher order terms through evaluation of within subclass bias effect sizes and other relevant PS diagnostic information; and (3) exclusion of subjects in one treatment group with insufficient 'covariate overlap'. The magnitudes of standardized effect sizes for group differences in linear, squares, and cross-product terms within subclasses provide key insight into what additional terms the PS model must have in order to achieve adequate within-subclass balance between treatment groups. Specific choices made during the model building process pose no concern for Type I error inflation because these analyses do not involve any outcome data. In this way the sequential model-building exercise should be viewed as part of the 'design of the observational study'. The result of the PS modeling process is an assignment of patients from both groups to sub classes defined on the basis of the estimated propensity scores. When certain diagnostic properties hold, the covariate distributions are identical between the investigational and control groups within each of the PS quintiles. Therefore, within PS quintile, patients are essentially equally likely to be in either group based on relevant covariates and analyses can proceed as if patients were randomized. This is accounted for by including a  $df=4$  factor for propensity score quintile in analysis of variance and regression models. The ability of the propensity score model to balance observed covariates will be graphically assessed.

#### 2.2.6.6 SUPERIORITY TESTING

If the non-inferiority study success criterion is met, superiority testing will be performed in the intent-to-treat analysis set. It will be concluded that the Simplify® Disc is superior to the ACDF control if the PS-quintile adjusted one-sided p-value determined from the multiple imputation is less than 0.05.

#### 2.2.6.7 ADDRESSING MISSING OUTCOME DATA

Because of the availability of subject level data in controls that correspond to the subject level data to be collected in the prospective study, missing data will be addressed in the same fashion to how missing data would have been addressed in a randomized clinical trial. Multiple imputation will be used to impute missing final NDI in patients otherwise evaluable for primary CCS. For each of 20 imputed data sets, the primary PS stratified device group difference will be made resulting in a standard error for each. The final device group difference will be the average of the multiple imputed datasets and its standard error will account for both within (usual) and between imputation error.

In addition to multiple imputation, sensitivity analysis will be provided based on tipping point analyses. These are analyses in which all possible combinations of successes and failures are assumed for patients missing primary CCS and the fraction of scenarios in which the statistical conclusion changes is summarized. Best case and worst case, all missing success, and all missing failures scenarios will also be summarized.

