Subjects will be considered enrolled in the study for the purposes of an intent-to-treat analysis, only after they have been treated (time of incision). Subjects excluded prior to treatment, due to withdrawal of consent, arising medical difficulties (e.g., heart attack), documentation of ineligibility by circumstances unforeseen at the time of Consent, etc. will be considered screening failures. Baseline data, including the reason for exclusion, will be collected for screening failures. However, baseline data for screen failures may not be complete, as the patient may be determined to be a screen failure early in the screening process. All patients enrolled in the study will be included in an "intent to treat" analysis, regardless of failure to complete the required follow-up examinations.

All radiographic endpoints, including in vivo endplate thickness analysis, will be evaluated independently by one core laboratory. Range of Motion will be measured by this core lab using a protocol to determine this measurement incorporating validated computerized techniques to ensure reproducibility.

Neurologic status will be evaluated by a qualified evaluator, who may be an MD, an RN or a PA.

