## 2.2.6 STATISTICAL CONSIDERATIONS

### 2.2.6.1 PRIMARY ENDPOINT

The study hypothesis is that in subjects with DDD defined as intractable radiculopathy (arm pain and/or a neurological deficit) with or without neck pain or myelopathy due to a single-level abnormality localized to the level of the disc space at one level from C3 to C7 that is unresponsive to conservative management, the Month 24 composite clinical success (CCS) rate of the Simplify® Disc will be no worse than conventional ACDF when success of ACDF is evaluated at Month 24.

- Individual success for the investigational Simplify® Disc is defined as at least a 15 point improvement in NDI Score at 24 months compared with baseline, maintenance or improvement in neurologic status at 24 months compared with baseline, no device failures or revision, reoperation, removal and/or supplemental fixation within 24 months of index procedure; and the absence of major adverse events within 24 months as defined in Section 2.2.6.1 of this protocol.
- Individual success for the control ACDF device is defined as at least a 15 point improvement in NDI Score at 24 months compared with baseline, maintenance or improvement in neurologic status at 24 months compared with baseline, no device failures or revision, reoperation, removal and/or supplemental fixation with 24 months; and the absence of major adverse events within 24 months as defined in Section 2.2.6.1 of this protocol.

Device failure is defined as breakage, migration, or mechanical failure of the components as defined in the Radiographic Evaluation Protocol.

For purpose of determining individual subject success, a major adverse event is defined as any of the following which are definitely related to the device system or to a device component as determined by the CEC:

- Permanent neurologic damage or permanent nerve root injury related to a level at or below the level treated;

- Implant or component breakage or migration that does not require revision, reoperation or removal, but causes persistent or moderate to severe dysphagia and/or
- Subject death.

Per FDA Guidance for the Preparation of IDEs for Spinal Systems, the following definitions apply:

- Reoperation - any surgical procedure at the index level that *does not involve* modification, addition or removal of any components of the device” in the postoperative or follow-up period.

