#### 2.2.6.2 STUDY SUCCESS

The null hypothesis is that the probability of achieving Month 24 composite clinical success (CCS) for patients implanted with the Simplify® Disc device is no more than 0.10 smaller than the probability of ACDF control patients achieving Month 24 CCS. This study will be considered a success if the PS-quintile adjusted, multiple imputation based, 1-sided p-value for rejecting this null hypothesis is less than 0.05.

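### The deciding test imputes only a missing Month-24 NDI in patients otherwise evaluable; on the more natural reading, event-free patients who miss the Month-24 visit have no outcome in it, which conflicts with the intent-to-treat superiority test.

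*Combined protocol and SAP*

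**What the plan says.** **The deciding test.** Section 2.2.6.2 (Study Success) rests success on a propensity-score (PS) adjusted, "multiple imputation based, 1-sided p-value for rejecting this null hypothesis is less than 0.05". It names no analysis set.

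**The imputation.** Section 2.2.6.7 describes one imputation: "Multiple imputation will be used to impute missing final NDI in patients otherwise evaluable for primary CCS". Nothing visible defines the qualifier *otherwise evaluable*. The tipping-point, best/worst-case, all-success and all-failure analyses in the same section do give outcomes to patients missing CCS, but they do not decide success.

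**The endpoint.** Besides the 15-point NDI improvement, Section 2.2.6.1 requires "maintenance or improvement in neurologic status at 24 months compared with baseline". It separately lists the device and surgical events that must not occur: "no device failures or revision, reoperation, removal and/or supplemental fixation within 24 months of index procedure". A major adverse event also counts as failure. Section 2.2.7.6 has the Clinical Events Committee judge the neurologic component from the status at 24 months. Sections 2.2.5.4.3 and 2.2.5.5 schedule the NDI and the neurologic evaluation at the same Month-24 visit.

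**The population.** Section 2.2.4.1 puts all enrolled (treated) patients in an intent-to-treat analysis "regardless of failure to complete the required follow-up examinations". Section 2.2.6.6 runs the superiority test in the intent-to-treat set, using the multiple-imputation p-value.

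**The amount missing.** Section 2.2.6.4 reports that "116 of 133 (87.2%) ACDF controls were evaluable for Month 24 CCS" and reduces the 150 Simplify patients by 15% for loss to follow-up.

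**The concern.** A patient with no known failure who misses the Month-24 visit lacks two CCS components, the NDI and the neurologic status. Such a patient is not naturally evaluable apart from the NDI, so the imputation rule does not reach them. Known failures stay in, as do attendees who lack only the NDI, while event-free patients who miss the visit leave. Whether a patient enters the deciding test would then depend on follow-up, and partly on outcome.

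The PS quintiles balance baseline covariates (Section 2.2.6.5). They do not correct for later selection by follow-up, here in two studies run years apart.

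The rule also does not fit the stated populations. Superiority cannot be tested in the intent-to-treat set if the imputation that feeds it leaves some of that set without an outcome. For non-inferiority the conflict is only by implication, because Section 2.2.6.2 names no set.

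**Working it through.** **1. The plan's own power (Section 2.2.6.4).** Inputs: 115 Simplify and 93 control patients, rates 0.814 (0.741 + 0.073) and 0.741, margin 0.10, one-sided 0.05.

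SE = sqrt(0.814×0.186/115 + 0.741×0.259/93) = 0.0581. Power = Φ(0.173/0.0581 − 1.645) = 0.908, which reproduces the stated 91%.

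With an outcome for every patient kept after trimming (150×0.9 = 135 and 133×0.8 = 106), power would be 0.939. The issue is therefore bias, not power.

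**2. Patients at stake.** Controls: 133 − 116 = 17, and 17/133 = 12.8%. Simplify: 150×0.15 = 22.5, about 22. After trimming: 106 − 93 = 13 controls and 135 − 115 = 20 Simplify patients. These are upper limits. The documents do not split the 17 into missed visits and missing NDI alone, and the 15% is a planning figure.

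**3. Illustrative error rate at the null boundary.** Success among the missing, r, is not in the documents; I assume 50% or 60%. True rates in all kept patients are set to p1 = 0.641 and p0 = 0.741, a difference of exactly −10 points. With left-out shares f1 = 0.15 and f0 = 0.128, the rate among analysed patients is (p − f×r)/(1 − f). A non-informative loss leaves p unchanged.

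Example: Simplify missing at 50% gives (0.641 − 0.15×0.5)/0.85 = 0.6659. With 115 v 93 patients, SE = 0.0632 and the error is Φ((0.6659 − 0.741 + 0.10)/0.0632 − 1.645) = 0.105.

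| Assumed success among the missing | Analysed rates (Simplify v control) | One-sided error |
|---|---|---|
| Simplify 50%, control loss non-informative | 0.6659 v 0.741 | 10.5% |
| Simplify 60%, control loss non-informative | 0.6482 v 0.741 | 6.3% |
| Both 50% | 0.6659 v 0.7763 | 3.5% |
| Both 60% | 0.6482 v 0.7617 | 3.1% |
| Control 60%, Simplify loss non-informative | 0.641 v 0.7617 | 2.4% |
| Control 50%, Simplify loss non-informative | 0.641 v 0.7763 | 1.4% |

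The calculation uses an unpooled normal test and ignores the PS stratification.

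**4. The conclusion at the planned rates.** Analysed patients show +7.3 points. The rate in all kept patients is (1 − f)×p + f×r, tested with 135 v 106 patients.

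| Success among the missing (Simplify, control) | Difference, all kept |
|---|---|
| 50%, 74.1% | +2.6 points (z = 2.25) |
| 60%, 74.1% | +4.1 points |
| 50%, 50% | +5.7 points |
| 60%, 60% | +5.9 points |
| 81.4%, 50% | +10.4 points |

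The smallest z against the margin is 2.25, above the critical 1.645.

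Break point with missing controls at 74.1%: about 94 of 115 analysed Simplify patients succeed (115×0.814 = 93.6). If 5 of the 20 missing succeed, the rate is 99/135 = 0.733 and z = 1.617, so non-inferiority is lost. With 6 of 20, z = 1.754 and it holds.

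**The case against.** The strongest reply is that the text shows an undefined phrase, not an exclusion rule.

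- **A broader reading exists.** Section 2.2.7.6 defines neurologic failure as a decline that persists to 24 months, and the earlier control endpoint in Section 2.2.6.4 asks for no neurological deterioration. Either could let no recorded decline count as maintained; dropouts would then lack only the NDI and be imputed. This stands as a possibility, but no visible passage adopts it.
- **The sample-size text.** Section 2.2.6.4 expects imputation to lift the effective control sample slightly above 93. That shows some of the 17 were expected back, but it fits either reading.
- **The general intent-to-treat statement.** Section 2.2.4.1 does not say that its intent-to-treat analysis is the deciding one, so it fits the rule poorly rather than contradicting it. The firm conflict is with Section 2.2.6.6.
- **Sensitivity analyses.** They do cover these patients. That limits the harm but does not settle the test that decides success.
- **Redaction.** Sections 2.2.6.9 and 2.2.6.10 are blacked out and may define evaluability or analysis sets. This cannot be checked and is not held against the plan.
- **The error rates.** They rest on assumed success among the missing, and the 10.5% needs informative loss in the Simplify arm alone. This is right, and they are offered only as illustration.

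A reader might infer that the plan definitely excludes dropouts, or that its type I error is inflated. The documents support neither: the qualifier is open, and the error falls below 5% in four of the six cases shown.

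**Conclusion.** The point holds in limited form and should be fixed. On the more natural reading of Section 2.2.6.7, event-free patients who miss the Month-24 visit have no outcome in the deciding test. This conflicts with the superiority test in the intent-to-treat set. At most 12.8% of controls and about 15% of Simplify patients are affected.

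The direction of any bias is unknown. The illustrative error runs from 1.4% to 10.5% against a nominal 5%, entirely on assumed success of 50-60% among informatively missing patients.

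A reader might also infer that the non-inferiority conclusion is in danger or that the power is misstated. Neither follows. At the planned rates non-inferiority holds in every case listed, and with missing controls at 74.1% it is lost only if 5 or fewer of 20 missing Simplify patients succeed. The 91% power is correct. Confidence is medium, because the phrase is undefined and two sections are redacted.

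**What to change.** Replace the imputation sentence in Section 2.2.6.7 with:

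> For every treated patient kept in the PS design whose CCS is not already determined by a known failure, the missing CCS outcome (Month-24 NDI and neurologic status, or CCS success/failure directly) will be multiply imputed, separately by arm, from baseline and available interim NDI, neurologic and event data. Known failures stay failures.

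Name this one set for both the non-inferiority test (Section 2.2.6.2) and the superiority test (Section 2.2.6.6). Keep the planned sensitivity analyses. If the narrower rule is intended, define *otherwise evaluable* and state which patients it leaves out.

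**Cost.** New SAP wording and a somewhat larger imputation model, with no new data collection. NDI and neurologic evaluation are scheduled from 6 weeks and are not marked as investigational-only (Section 2.2.5.4.3). Section 2.2.6.3 states: "All components necessary to formulate the relevant composite clinical endpoints are available in both studies". That does not confirm complete interim neurologic data in controls, so the model should use what is available.

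**Downside.** The imputation relies on missing at random. It reduces the bias only as far as observed baseline and interim data explain the loss, and the documents do not show how far that is. The tipping-point analyses therefore remain necessary.
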